# 4.3.2 Surgery or Other Invasive Procedures

If the patient requires elective surgery or other invasive procedures with a risk of bleeding, the study medication should be stopped 7 days prior to the procedure and resumed the day after the procedure if there has not been inordinate bleeding and if the physician performing the procedure agrees. If the patient requires emergent surgery where the risk for bleeding is high (e.g., neurosurgery) the study medication should be stopped and consideration given to revealing the medication code and administering platelet transfusion if the patient has been receiving active drug.

#### 4.3.3 Other Adverse Events

Aggrenox has been associated with a higher incidence of headaches and GI disturbances, particularly diarrhea compared to placebo. However, these tend to get better with continued use of the drug (48). If these events occur, efforts should be made to treat them conservatively (e.g., acetaminophen for headache or psyllium for diarrhea) and continue the study medication. If the symptoms persist then a trial of withdrawing the study medication for a week can be performed to see if the symptoms resolve. If the symptoms do resolve and the subject agrees, rechallenge with the study medication should be considered to confirm that it is the cause of the symptoms before stopping the study medication completely. A committee of study investigators will review the reasons leading to permanent withdrawal from therapy.

#### 4.3.4 Concomitant Medications

The risk of bleeding is likely to be increased if Aggrenox is used in combination with anticoagulants or antiplatelet agents. In addition, the risk of GI complications including ulcers is likely to be increased by combined use of Aggrenox with nonsteroidal anti-inflammatory agents. Every effort should be made to avoid the use of anticoagulants (e.g., warfarin), antiplatelet agents (e.g., clopidogrel, ticlopidine or sulfinpyrazone) or nonsteroidal anti-inflammatory agents (e.g., ibuprofen) in patients while on study medication. If there is an absolute medical indication for any of these agents (e.g., anticoagulants for atrial fibrillation or deep venous thrombosis) then therapy with the study medication should be discontinued and the patient continued to be followed for the duration of the study. Likewise, if a medical requirement for Aggrenox or dipyridamole arises then the study medication will be stopped and the patient followed for the duration of stroke or myocardial infarction) or the use of intermittent heparin for hemodialysis will not constitute a reason for stopping the study medication. Management of pain should be attempted first with acetaminophen, codeine or other analgesics.

#### 4.3.5 Risk of Adenosine

The dipyridamole in Aggrenox can potentiate the action of adenosine used in some heart stress tests (e.g. adenosine-thallium nuclear medicine stress test). Adenosine is also occasionally used to block certain supraventricular arrhythmias. The study medication should be discontinued 2 days before using adenosine for cardiac function testing. The study medication can be restarted after the stress test is completed. Adenosine should be avoided or used cautiously in any study subject who develops a supraventricular tachyarrhythmia. Alternate methods of cardiac stress testing, such as dobutamine echocardiography are acceptable for subjects on the study medication.

#### 4.3.6 Discontinuation of Therapy

Adverse events leading to cessation of study drug, but not termination from the study will include:

- 1. Development of an intestinal ulcer or gastrointestinal bleeding while on the study medication.
- 2. An adverse event attributed to the study medication such as intolerable persistent headache, diarrhea or dizziness without other etiology that does not respond to medical management.
- 3. A bleeding disorder (e.g., a major or life-threatening bleed) that contraindicates the continued use of Aggrenox.
- 4. A new medical requirement for long-term anticoagulation or antiplatelet therapy other than aspirin.
- 5. A new medical requirement for using Aggrenox or dipyridamole.

#### 4.4 Events Leading to Withdrawal from the Study

A patient will be withdrawn from the study for the following reasons:

- 1. Death
- 2. Loss to follow-up due to permanent transfer to another renal replacement modality or to a nonparticipating dialysis unit.
- 3. Withdrawal of consent.

#### 4.5 Study Completion

Study participation will end at: 1) the first monthly visit following the primary endpoint, 2) patient withdrawal due to one of the reasons listed in Section 4.4, or 3) the end of the study. Study medication will be withdrawn at the time of the primary endpoint, patient withdrawal, and the end of the study. Total failure of the access site is defined as the complete cessation of function of the study access that cannot be restored and results in the need to place a new access at a distinctly different site (either catheter or arteriovenous shunt) to continue dialysis.

Data collection after study participation has ended will consist of the following: At completion of the study it will be determined whether the access that was randomized into the study is still functional or not. If total site failure has occurred, the date of that occurrence will be determined. Hospitalization and mortality data will be obtained using national databases while the study is on-going and for up to five years after the study has ended.

# 5. ACCESS FLOW MONITORING

#### 5.1 Rationale

Longitudinal observational studies have shown that an active access surveillance program can decrease the rate of graft thrombosis and may increase overall access survival (3, 23, 65, 66). Based on these studies, the guidelines from the Dialysis Outcomes Quality Initiative (DOQI) recommended an organized approach to access surveillance with regular assessment and tracking of access function to detect and treat access stenosis (3). Several approaches are used for access surveillance (3, 67) and there is currently no uniform approach to monitoring access function across all the Clinical Centers. Since the efficacy to detect stenosis before thrombosis varies between the different techniques, this may lead to heterogeneity in the event rate between units. For instance, dialysis units that use flow monitoring to detect access dysfunction are likely to detect access stenosis and refer a patient for a corrective procedure (the endpoint) earlier than units who use alternate surveillance strategies. The type of primary endpoint would also be affected, as programs with flow monitoring will have more angioplasties rather than thrombosis as the primary endpoint (68). Of the currently available techniques, routine monthly measurement of access flow rate offers the most accurate and practical technique to detect access stenosis (68). To promote uniformity between Clinical Centers, routine monthly flow monitoring was therefore chosen as the standard access surveillance technique for the study.

One major advantage of flow monitoring is the ability to make a better assessment of the mechanism of action of the study drug. This is something unique to the hemodialysis access that cannot be easily done in studies of other vascular beds. For instance, initial access flow rate may be an important inverse predictor of access failure (28, 69, 70). As a vasodilator, dipyridamole may act to increase (or decrease, if it causes a "steal" syndrome) the initial access flow rate and this might help explain the observed outcome. In addition, if dipyridamole acts to inhibit the development of access

stenosis this will be discovered by comparing the rate of decline of access flow rate between placebo and dipyridamole. The resulting fistulogram will then confirm anatomically the hemodynamic evidence of stenosis obtained from the access flow measurements. Thus access flow monitoring enhances our ability to detect a drug that inhibits vascular access stenosis. A potential concern is that routine flow monitoring leading to angioplasty of stenotic lesions prior to thrombosis may mask a potentially beneficial anticoagulant effect of a study drug. Nevertheless, access stenosis is the predominant underlying etiology of access thrombosis and access flow monitoring should enhance our ability to more rapidly and specifically detect pharmacological agents that inhibit this process. In addition, the enhanced accuracy to detect stenosis as the cause of access failure should improve secondary analyses of covariates that predict access stenosis.

#### 5.2 Procedure for Measurement of Access Flow

The technique for measuring access flow rate using the saline infusion ultrasound dilution technique is based on the Fick principle and has been detailed by [name] (see Manual of Operations). At each monthly visit the study coordinator will obtain one measurement of access recirculation while in the standard configuration for dialysis (i.e., blood is being withdrawn using the needle closest to the arterial anastomosis and returned in the needle that is farthest away from arterial anastomosis of the graft). Then the lines will be switched and two measurements of access blood flow obtained in this reverse configuration. If the two measurements differ by greater than 10%, then a third measurement will be obtained. These measurements must be within the first two hours after starting dialysis. All blood flow measurements will be reported to the DCC.

Changes in cardiac output and blood pressure will directly alter access blood flow (i.e., access flow increases with increased cardiac output and blood pressure) (117). Cardiac output and blood pressure are influenced by many external factors that may vary between dialysis sessions including medications, volume status, the rate of fluid removal on dialysis or a new cardiac event. This will introduce variability into the measurement of access flow. We can not easily measure cardiac output on a routine basis but blood pressure will be recorded at the time the access blood flow is measured. The blood pressure recorded at the time of access measurement will be used to normalize the measured access blood flow to a standardized mean arterial pressure of 90 mmHg using the equation nQb = mQb + ((90 - MAP)\*8.6)

where nQb is the normalized access blood flow, mQb is the measured access blood flow, MAP is the mean arterial pressure calculated as (DBP + ((SBP-DBP)/3)) and the factor 8.6 is derived from the published regression equation for access flow rate on mean arterial blood pressure (117). In addition, every effort will be made to obtain the access flow readings within the first hour after starting dialysis. The time of the access flow measurement as well as the dialysis start time will be recorded.

The mean value of all the normalized access flow measurements obtained at each visit will be calculated and used to determine if the patient meets criteria for access evaluation. Each month the change in normalized access flow will be calculated as the difference between the current month's mean normalized flow measurement and the average of the first two measurements. The first flow measurement will be obtained as soon as possible after starting to use the access but no more than two weeks after starting to use the access for dialysis. The second measurement will be obtained approximately two weeks later. This second measurement can be no sooner than 1 week nor more than 1 month after the first access measurement. Thereafter, access flow measurements will be obtained at least monthly preferably timed from the date of the first access flow measurement is found to meet criteria for access evaluation (see below) it is recommended that the results be validated with repeat flow measurement at a different dialysis session before sending the patient for angiography. This second confirmatory measurement should be done as soon as possible preferably within 2 weeks after the first measurement that met criteria for access evaluation.

#### 5.3 Access Management Based on Access Flow Data

Studies with access flow monitoring have demonstrated that for arm grafts, an access flow rate less than 600 ml/min or a drop in access flow rate of 25% when the access flow rate is less than 1,000 ml/min is predictive of hemodynamically significant access stenosis (28, 69, 70). Based on these parameters an algorithm for the monthly surveillance of access flow rates has been developed. The algorithm is shown in Figures 5.1 (Calculating Study Baseline) and 5.2 (Regular Monthly Measurements). The current visit's flow measurement will trigger consideration for an angiographic evaluation if: i) the nQb is <600 ml/min, or ii) the nQb is < 1000 ml/min and is at least 25% below the study baseline flow (see Fig. 5.1). If angiographic evaluation of the access reveals a stenosis of 50% or more then a corrective procedure, most likely angioplasty will be undertaken to reverse the stenosis. This represents the primary endpoint of the study.

If based on these flow criteria the patient is referred for an angiogram that fails to detect a significant access stenosis (i.e., less than 50% stenosis) then the subject will not have reached the primary endpoint. Failure to find an access stenosis when the flow rate has met the targets for access evaluation may be due to a drop in cardiac output (e.g., from volume depletion or a recent myocardial infarction), technical error in making the access flow measurement, or a false negative result with angiography (i.e., missing a stenosis that was actually present). If the flow measurement the next month still meets a target for access evaluation then a new baseline will be established based on an average of the three values prior to the procedure and the one after the procedure. A further drop in access flow rate of 25% below this new baseline or a drop below 600 ml/min (if not already at or below this level) will lead to another referral for angiography. Monthly flow monitoring will continue until one month after the primary endpoint (to determine whether the access procedure restores access flow) or until the study ends.

Figure 5.1

# Flow Diagram for AVG Surveillance - Calculating First Baseline

#### Figure 5.2

# Flow Diagram for AVG Surveillance - Regular Monthly Measurements

#### 5.4 Quality Control of Flow Monitoring

Quality control procedures for flow monitoring will include training flow monitoring technicians by manufacturer representatives and by ongoing review of the measurements (see Manual of Operations).

# 6. DATA COLLECTION

#### 6.1 Baseline Data

The baseline evaluation is designed to: 1) ensure that subjects meet the inclusion/exclusion criteria, 2) obtain information regarding demographics, access history, medications, and medical history that may affect treatment response and risk of access failure, and 3) obtain information on medical history and laboratory tests to ensure that patients are not at risk for developing

complications of therapy. Data should be collected as close to the time of graft creation as possible but no longer than 45 days prior, and should include:

- 1. Patient identification demographic information (age, gender, race)
- 2. Patient's mailing address for study medication. If no suitable home address, medication will be mailed to the dialysis unit to provide to the patient
- 3. Date of enrollment
- 4. Date of ESRD; start date for hemodialysis
- 5. Cause of ESRD (diabetes, hypertension, polycystic kidney disease, glomerulonephritis, interstitial nephritis, hereditary nephritis, other)
- 6. Access history
  - a. Prior arteriovenous access attempts number, type, location, date(s) placed
  - b. Prior central catheter placements (subclavian or int. jugular) yes/no; right, left or both
    c. Current central catheter type, site, date placed
- 7. Diagnoses (history of diabetes (duration, nephropathy, retinopathy, neuropathy), hypertension (duration), vascular disease (myocardial infarction, CABG, CHF, angina, stroke, TIAs, peripheral vascular disease, amputations), coagulopathy, or hyperlipidemia
- 8. List of current medications
- 9. Tobacco use (how much, age at start, currently smoking (yes/no), if not, when habit stopped
- 10. Quality of life questionnaire
- 11. Blood pressure & pulse predialysis, sitting position
- 12. Height and weight
- 13. Periodontal disease (no obvious cavities or gingivitis, cavities or gingivitis, or edentulous)
- 14. Examine arms to note scars and evaluate number and location of any current functional accesses and previously failed access sites
- 15. Look for presence of current central catheter Note type and location.
- 16. Baseline biochemical measurements most recent within the last 45 days, record date CBC (hemoglobin, platelet count), and albumin.

#### 6.2 Monthly Visits

The purpose of monthly visits is to: 1) assess access function and monitor for the development of access stenosis using flow monitoring, 2) obtain information on all access-related events and procedures relevant to the primary and secondary outcomes, 3) determine whether there have been changes in the medical condition or medications that might influence access survival or require discontinuation of the study medication, 4) report any adverse complications of the study medication

5) assess and encourage compliance with the study medication and follow-up. All the data elements listed in Section 6.2.2 below will be collected at each monthly visit up to the primary endpoint. Additional data elements will be collected at the first visit and at each third visit as listed below.

# 6.2.1 First Monthly Visit

At the first visit after creation of the access data on the type of graft material used and the location and configuration of the graft will be collected. In addition, the date of surgery and the surgeon will be confirmed. The date of first cannulation of the access for dialysis will be recorded as soon as it is available.

# 6.2.2 All Monthly Visits

- 1. Access recirculation and access blood flow within first 2 hours of dialysis (see Manual of Operations)
- 2. Blood pressure (sitting) predialysis (from chart) and at time of access blood flow
- 3. Person doing needle insertion (patient or nurse).
- 4. Problems with needle insertion in the last month (hematomas, multiple needle sticks, failed insertions)
- 5. Access related events (see list in Section 12.1)
- 6. Access related procedures (see list in Section 12.2) indication, date of procedure, outcome
- 7. Hospitalizations primary and secondary diagnosis, dates of admission and discharge
- 8. Compliance with study medications as assessed by patient interview and monthly pill count. Subjects will be asked to return pill bottles of study medication each month.
- 9. Current medications.
- 10. Monthly dialysis lab tests serum albumin, hemoglobin, hematocrit, pre and post BUN, calcium, phosphorus. PTH when available every third month.
- 11. For incident patients not yet on dialysis the patency of the access will be determined by the presence of an audible bruit or a palpable thrill in the graft.
- 12. Adverse event monitoring (see Section 6.2.3 below)

# 6.2.3 Monthly Adverse Event Monitoring

Adverse events will be recorded at the monthly visits. Subjects will be asked the following questions:

- 1. Have you had any problems with your study medication? Describe them.
- 2. Have you had any hospitalizations? When and what was the reason?
- 3. Have you had any other new significant health problems? Describe them.
- 4. Have you had any episodes of significant bleeding?
- 5. Are you having any gastrointestinal symptoms such as heartburn or abdominal pain?

The responses to all these questions will be recorded and an assessment will be made as to whether the event is related to the study medication. For any hospitalizations or emergency room visits the medical record will be reviewed to determine the cause of the visit and whether it was likely related to the study medication. Particular attention will be given to whether a bleeding event precipitated the visit or hospitalization. For patients that might be questionable historians, the dialysis nurse caring for the patient will be asked whether they are aware of any adverse events, hospitalizations, or transfusions that have occurred in the preceding month. In addition, the patient dialysis logs will be examined to determine if the patient missed any sessions and the patient will be asked the reason for the absence. Serious adverse events are those that result in any of the following outcomes: death, a life-threatening adverse experience, inpatient hospitalization or prolongation of existing hospitalization, a persistent or significant disability/incapacity, or a congenital anomaly or birth defect. All serious adverse events will be reported to the DCC within 24 hours of study personnel learning of the event.

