#### 4.3.1 Bleeding

Aggrenox has a small dose of aspirin that will increase the risk of bleeding. Bleeding will be classified as either minor, intermediate, major, life-threatening or fatal. Minor bleeding events are episodes of bleeding that did not require an event-related visit or follow-up or discontinuation of the study drug. Intermediate bleeding is a bleeding event that does not meet criteria for a major bleed but required an event-related visit with a health care provider or temporary discontinuation of study medication. Examples of minor or intermediate bleeds might include superficial cuts, abrasions, bruises, nose bleeds, or vaginal bleeding events. The presence of a hemoccult positive stool alone that leads to non-emergent evaluation such as a colonoscopy and is not associated with a 2 g/dl drop in hemoglobin or the need for a transfusion will be considered an intermediate bleeding event. Major bleeding is defined as a confirmed retroperitoneal, intra-articular, intraocular, or intracranial bleed or any bleed that leads to a drop in hemoglobin by 2 g/dl and requires hospitalization or the need for a transfusion, causes a symptomatic intracranial hemorrhage, or requires a transfusion of more than 4 units of packed RBCs or whole blood. Fatal bleeding is any bleed that causes or precipitates death.

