Management of bleeding should be handled as for a patient on aspirin. For minor episodes of bleeding (e.g., superficial abrasion or nose bleed) conservative measures to control the bleeding should suffice without the requirement for discontinuing study medication. Short-term discontinuation of study medication during an intermediate bleeding episode with re-institution when stable is allowed. If the patient has a major or life-threatening bleed the study medication will be discontinued and not restarted. In the event of a cerebrovascular accident occurring during active treatment, computed tomography or magnetic resonance imaging should be performed to exclude intracerebral hemorrhage. For intermediate bleeds the decision to stop study drug will be made by the physician(s) caring for the patient. If the patient has a major or life-threatening bleed the study medication will be discontinued and not restarted unless the bleed is caused by either a surgical procedure or trauma and it is established 1) that the cause of bleeding has been eradicated, and 2) that the bleeding event does not reflect an underlying bleeding tendency or predispose to recurrent bleeding. Study drug resumption in this situation must be approved by the physician(s) caring for the patient. Bleeding events will be actively monitored and recorded by the study coordinator throughout the patient's participation on the study. An expert panel will review all major and life-threatening bleeds as well as a randomly selected subset of other bleeding events.

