#### 8.2 Patient Survival

It is important that the study drug not produce any adverse consequences that might be worse than the measured outcome. Aspirin contained in Aggrenox is expected to cause an increase in minor and major bleeding events but is not expected to increase serious or fatal bleeding events. On the other hand, aspirin is known to decrease the rate of arterial thrombotic events in high risk populations. Given the high rate of cardiovascular death in the hemodialysis population, aspirin might actually improve overall patient survival. Due to the importance of this issue, time from randomization to death has been designated as a secondary outcome variable. However, it is recognized that the power of the study to detect a treatment effect on mortality is limited.

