# 12. ACCESS RELATED EVENTS AND PROCEDURES

#### 12.1 List of Access Events that Might Lead to Access Evaluation

- 1. Meets flow surveillance criteria for possible stenosis (see flow surveillance algorithm)
- 2. Thrombosis (loss of palpable access flow)
- 3. High venous pressures
- 4. Inability to achieve desired blood flow rate
- 5. Excessive bleeding post needle removal
- 6. Lower than desired kT/V
- 7. Inability to cannulate access
- 8. Access pain
- 9. Infection
- 10. Aneursym
- 11. Pseudo-aneursym
- 12. Arm swelling

- 13. Ischemia of distal extremity
- 14. High output state
- 15. Access hemorrhage
- 16. Neurological changes in access arm
- 17. Other

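### The only monthly patient question that names bleeding is limited to an undefined 'significant' bleed, so lesser bleeds that the protocol classifies and expects to increase are likely to be under-counted and unevenly recorded.

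*Protocol*

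**What the plan says.** **Classification.** Section 4.3.1 sets five classes: "Bleeding will be classified as either minor, intermediate, major, life-threatening or fatal". The lowest is defined by the absence of any consequence: "Minor bleeding events are episodes of bleeding that did not require an event-related visit or follow-up or discontinuation of the study drug". The intermediate class covers bleeds that led to a health-care visit or a temporary drug stop without meeting the major criteria. Bruises and nose bleeds are among the examples of minor or intermediate bleeds.

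**Commitment to record.** The same section says "Bleeding events will be actively monitored and recorded by the study coordinator" and sets no severity threshold. An expert panel is to review all major and life-threatening bleeds "as well as a randomly selected subset of other bleeding events", so lesser bleeds are meant to reach the database.

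**Expectation.** Section 8.2 states: "Aspirin contained in Aggrenox is expected to cause an increase in minor and major bleeding events". Section 6.2.6 treats bleeding as the main risk expected from the drug.

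**Collection.** Section 6.2.3 lists five questions for the patient. Question 4 is the only one that names bleeding: "Have you had any episodes of significant bleeding". Section 6.2.2 separately collects, each month, needle-insertion problems including hematomas, and the access events of 12.1. Item 5 of that list is "Excessive bleeding post needle removal" and item 15 is hemorrhage from the access.

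**The concern.** The classification and the question do not fit each other. A patient asked about *significant* bleeding has to supply a personal threshold, and in ordinary use that threshold sits above a nose bleed or a bruise. Question 5 in the same list asks about gastrointestinal symptoms without a severity limit and gives examples, so a broader form was available. The harm the protocol worries about most is the one asked about with a threshold and no prompts.

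A bleed that is never elicited cannot be classified under 4.3.1 or drawn into the panel's sample, and no later analysis can recover it. At stake are the completeness of the lesser-bleed counts, the size of the absolute difference between arms in those classes, and comparability between patients and centers that read the word differently.

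**Working it through.** The protocol gives no figure for this point, so the main check sets the collection routes beside the classes they must feed.

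**Routes that could pick up a minor or intermediate bleed away from the access**

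| Route (Protocol section) | Reach | Gap |
|---|---|---|
| Question 4 (6.2.3) | Bleeding, by name | Limited to an undefined threshold |
| Question 1 (6.2.3) | Any problem with study drug, no severity limit | A masked patient must attribute the bleed to the capsule; 1.5 reports that about 30% of hemodialysis patients in the investigators' units already take aspirin |
| Question 3 (6.2.3) | Other new health problems | Again limited to significant ones |
| Hospital and emergency-room record review (6.2.3) | Bleeds leading to such a visit | By definition no minor bleed; misses intermediate bleeds handled as outpatients, such as the 4.3.1 example of a positive stool test followed by a non-emergent colonoscopy |
| Dialysis nurse (6.2.3) | Any adverse event | Only for patients whose history is thought unreliable |
| Needle-site hematomas and 12.1 access events (6.2.2) | Every patient, every month | Access bleeds only; no sentence carries them into the 4.3.1 classes |
| Coordinator's active monitoring (4.3.1) | All bleeding events | Names no question or form item by which it is done |

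Some lesser bleeds will be recorded. No route in the text asks every patient, without a threshold, about bruises, nose bleeds and similar events.

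**Indicative scale.** The bleeding table in 1.5 gives, for placebo and for dipyridamole plus aspirin:

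- all bleeding: 74 and 144, excess 144 − 74 = 70;
- severe or fatal: 7 and 27, excess 27 − 7 = 20;
- below severe, by subtraction: 67 and 117, excess 50.

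Share of the excess below severe: 50/70 = 71%. The table's percentages agree: (8.7 − 4.5) − (1.6 − 0.4) = 3.0 points, and 3.0/4.2 = 71%. Share of active-arm bleeds below severe: 117/144 = 81%.

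**What partial reporting would do.** Assume that all severe bleeds are reported, and that a fraction *r* of the others is reported, equal in both arms. The observed excess is 20 + 50*r*, and the proportion of the true excess lost is (50/70)(1 − *r*).

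| *r* (assumed) | Observed excess | Excess lost | Ratio (27 + 117*r*)/(7 + 67*r*) |
|---|---|---|---|
| 1 | 70 | 0% | 144/74 = 1.95 |
| 0.5 | 45 | 36% | 85.5/40.5 = 2.11 |
| 0 | 20 | 71% | 27/7 = 3.86 |

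Equal under-reporting shrinks the absolute difference while the all-bleeding ratio rises. Within the lesser class the ratio stays at 117/67 = 1.75 for any *r* above 0, and the difference falls in proportion to *r*. The protocol gives no value for *r*.

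**The case against.** The strongest reply is that question 4 is one prompt among several. Question 1 has no severity limit, the nurse inquiry covers any adverse event, and hematomas, post-needle bleeding and access hemorrhage are collected every month. Section 4.3.1 commits the coordinator to record bleeding without a threshold and does not exclude access bleeds from its classes. Section 6.2.6 says bleeds are categorized from data forms and source documents. Those forms are not at hand, so the five questions cannot be shown to be the whole instrument.

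The consequence is also limited. Minor bleeding is neither a primary nor a secondary outcome. Major and life-threatening bleeds go to expert review, admissions and emergency visits have their records read, and a bleed recorded within 30 days before death has central review. Treatment is masked, so under-reporting should be broadly similar by arm.

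Most of this stands. A reader might infer that the question screens out minor bleeding altogether, that the back-up sources see only large events, or that the instrument cannot measure the class. The text does not support these readings, because the routes above can each catch some lesser bleeds. A reader might also take 71% as the expected loss. It is an upper bound on another trial's scale, where severe meant a transfusion, and it assumes that no lesser bleed is reported by any route. Nor do the documents say that most of the excess falls in the minor class: the 1.5 table does not separate minor from intermediate, and 8.2 does not apportion the increase.

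The reply does not remove the mismatch itself. Masking makes under-reporting similar by arm but does not preserve the absolute difference or give patients and centers a common threshold.

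**Conclusion.** The point holds as a mismatch between an undefined threshold in question 4 and the five-class scheme, the recording commitment and the expected increase in minor bleeding. The likely effect is under-ascertainment and inconsistent recording of minor, and some intermediate, non-access bleeds.

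The observed absolute difference in lesser bleeds would be too small by an amount the documents cannot size. The range of 0 to 71% of the all-bleeding excess is illustrative. It rests on carrying over the stroke-prevention trial's severity split, on full reporting of severe bleeds and on equal reporting by arm. The conclusion also assumes that patients read *significant* in its ordinary sense and that no form outside the protocol asks more broadly.

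This is a cheap improvement of modest consequence: it bears on the safety comparison for the drug's main named risk, but not on the primary outcome or on the detection of major and fatal bleeds.

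**What to change.** In 6.2.3, reword question 4 to ask about any bleeding or bruising since the last visit, however small, with brief prompts such as nose, gums, skin, stool and prolonged bleeding after needle removal. Have the coordinator, not the patient, judge severity by assigning the 4.3.1 class. Add one sentence stating that items 5 and 15 of 12.1 are also classified as bleeding events under 4.3.1.

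If a data form already captures lesser bleeds, it would be enough to say that question 4 is only a screen and to name the item that does so.

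The cost is one reworded question, one added sentence and more minor-event forms at monthly visits. Treatment rules and outcomes are unaffected.
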